The side-effects experienced by both orlistat and acarbose are various gastrointestinal symptoms (such as flatulence, stomach rumblings, abdominal pain, increased defaecation, liquid and/or oily stools) as well as headache and nausea. Upper respiratory infections have also been reported to be more frequent with orlistat [15]. However, these side-effects are transient and will quickly resolve if patients stop taking the drugs. In rare cases, effects on the liver after taking acarbose have been reported [29]. For that reason, blood samples are taken at every visit to analyse liver function parameters.

Besides the risks related to the IMP as described above, there may also be risks related to the medical devices used in the study, for *e.g.*, venepuncture. However, these are devices that are

CONFIDENTIAL 25 (92)

Clinical Study Protocol EP-002 Final version v3.0 12NOV2020

used in routine medical care and the risk associated with their use is considered low and ethically justifiable. Study specific evaluations and sampling procedures, like blood pressure measurements using a blood pressure cuff and frequent blood sampling, may cause transient discomfort but the risk is deemed to be low and ethically justifiable.

Overall, the combined safety data from the previous phase IIa trial [28], and other pre-clinical and clinical studies, have not revealed any safety issues that would outweigh the expected benefits of the study. While keeping the above-mentioned risk factors at a minimum level in order to not expose the patients participating in the study for risks that would not be ethically justifiable, it is concluded that the planned study assessments are considered sufficient to meet the scientific and medical goals for the study. With regard to the substantial medical need for treatment of obesity, it is concluded that the potential benefits from the study will outweigh the potential risks for the treated patients.

More detailed information about the known and expected benefits and risks and reasonably expected adverse events (AEs) of EMP16-02 is found in current version of the IB.

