To assess the effect of two different doses of EMP16-02 (120 mg O/40 mg A and 150 mg O/50 mg A) on blood pressure during a 26-week period of oral treatment as compared to placebo.	Relative (%) and absolute change from baseline in blood pressure after 14 and 26 weeks of treatment with EMP16-02 (120 mg O/40 mg A and 150 mg O/50 mg A) as compared to placebo.	Blood pressure measurement (Section 11.5.3)
To assess the effect of two different doses of EMP16-02 (120 mg O/40 mg A and 150 mg O/50 mg A) on quality of life during a 26-week period of oral treatment as compared to placebo.	Change from baseline in quality of life after 26 weeks of treatment with EMP16-02 (120 mg O/40 mg A and 150 mg O/50 mg A) as compared to placebo.	Health and life quality questionnaire RAND-36 (Section 11.5.4.5) Activity and sleep questionnaire (Section 11.5.4.4)
To assess the relationship between dropout(s) and tolerability for two different doses of EMP16-02 (120 mg O/40 mg A	Dropout rate (overall and GI-related) following treatment with EMP16-02 (120 mg O/40 mg A and 150 mg O/50 mg A) as compared to placebo.	Careful collection of reason for early discontinuation

CONFIDENTIAL 30 (92)

Clinical Study Protocol EP-002 Final version v3.0 12NOV2020

	Objective	Endpoint	Assessment(s)
	and 150 mg O/50 mg A) during a 26-week period of oral treatment as compared to placebo.		
	To assess the safety and GI tolerability of two different doses of EMP16-02 (120 mg O/40 mg A and	Frequency and severity of AEs during 26 weeks of treatment with EMP16-02 (120 mg O/40 mg A and 150 mg O/50 mg A) as compared to placebo.	AE questioning (Section 11.6.1)
	150 mg O/50 mg A) during a 26-week period of oral treatment as compared to placebo.	Clinically significant relative (%) and absolute changes from baseline in safety laboratory parameters and electrocardiogram (ECG) after 26 weeks of treatment, and in vital signs after 7, 14 and 26 weeks of treatment with EMP16-02 (120 mg O/40 mg A and 150 mg O/50 mg A) as compared to placebo. GI tolerability after 2, 4, 6, 8, 14 and 26 weeks of treatment with EMP16-02 (120 mg O/40 mg A and 150 mg O/50 mg A) as compared to placebo.	Vital signs (Section 11.6.3) 12-lead ECG (Section 11.6.4) Blood sampling for assessment of safety laboratory parameters (Section 11.6.5) GSRS (gastrointestinal symptom rating scale, Section 11.5.4.2)

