	Alcohol breath test	11.3.7	X	X	X	X	X	X			
	Pregnancy test ³	11.3.8	X	X	X	X	X	X			
	Urine drug screen ⁴	11.3.9	X					X			
Weight-related	Weight	11.4.1	X	X	X	X	X		X		
assessments	Height	11.5.1.1	X								
	BMI	11.5.1.1	X	X		X	X		X		
	Waist circumference	11.5.1.2	X	X	X	X	X				
	Sagittal diameter	11.5.1.3	X	X	X	X	X				
	Bio-impedance	11.5.1.4		X	X	X	X				

CONFIDENTIAL 37 (92)

Clinical Study Protocol EP-002 Final version v3.0 12NOV2020

Category Visit		Refer to CSP		Follow-up part					
		Section	Screening		Safety follow-up	6 month follow-up			
			Visit 1	Visit 2 ¹	Visit 3 ¹	Visit 4 ¹	Visit 5 ¹	Visit 6	Visit 7 ¹³
			Morning visit	Morning visit	Morning visit	Morning visit	Morning visit	Morning visit	Morning visit
	Assessment		Day -28 to Day -1	Week 1	Week 7	Week 14	Week 26	Week 28 ²	Week 52 (±2 weeks)
				Day 1 Baseline	Day 46 (±3 days)	Day 95 (±3 days)	Day 179 (±3 days)	Day 193 (±3 days)	
Blood and urine sampling	Full safety laboratory profile ⁵	11.6.5	X					X	
(fasting)	Liver function ⁶	11.6.5		X	X	X	X		
	HbA1c, glucose, insulin, triglycerides, total cholesterol, LDL, HDL, Hs-CRP, albumin	11.5.2		X	X	X	X		X ¹⁵
	Exploratory: ApoA1, ApoB	11.7.1		X	X	X	X		
	Exploratory: Blood sampling for orlistat and acarbose plasma levels ⁷	11.7.2					X		
Vital signs and	Vital Signs	11.6.3	X	X	X	X	X	X	X ¹⁶
ECG	12-lead ECG	11.6.4	X					X	
Questionnaires	Meal pattern	11.5.4.1		X	X	X	X		
	GI tolerability (GSRS) ⁸	11.5.4.2		X	X	X	X		
	Satiety and craving ⁹	11.5.4.3		X	X	X	X		
	Activity and sleep	11.5.4.4		X	X	X	X		
	Health and quality of life RAND-36 ¹⁰	11.5.4.5		X			X		

CONFIDENTIAL 38 (92)

Clinical Study Protocol EP-002 Final version v3.0 12NOV2020

Category Visit		Refer to CSP			Main	part			Follow-up part
		Section	Screening			Safety follow-up	6 month follow-up		
			Visit 1	Visit 2 ¹	Visit 3 ¹	Visit 4 ¹	Visit 5 ¹	Visit 6	Visit 7 ¹³
			Morning visit	Morning visit	Morning visit	Morning visit	Morning visit	Morning visit	Morning visit
Assessment	Assessment		Day -28 to Day -1	Week 1	Week 7 Day 46 (±3 days)	Week 14 Day 95 (±3 days)	Week 26 Day 179 (±3 days)	Week 28 ² Day 193 (±3 days)	Week 52 (±2 weeks)
				Day 1 Baseline					
IMP	Randomisation	9.9		X					
	Dispense IMP			X	X	X			
	IMP administration at clinic ¹¹	10.5		X	X	X	X		
	IMP compliance	10.7			X	X	X		
Food	Standardised breakfast ¹²			X	X	X	X		
Patient	Diary instruction	11.2		X					
instructions	Diet recommendations	9.6.1.2		X					
AEs and	Baseline symptoms	11.3.10	X	X					
medication	AEs	11.6.1				X			

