	Prior and concomitant med.	11.3.5				X			

CSP=Clinical study protocol, HIV=Human immunodeficiency virus.

- 1. For detailed schedule of events, see Table 8.1-4.
- 2. At Visit 6 or after early withdrawal.
- 3. Women of child-bearing potential (WOCBP) only, urine test.
- 4. Drug tests may also be performed at additional random occasions during the study.
- 5. Full safety laboratory profile: Clinical chemistry, haematology, coagulation, urinalysis (dip stick). Fasting is not required prior to Visit 1 and Visit 6.

6. Liver enzymes: ALT, AST, ALP, GGT.

CONFIDENTIAL 39 (92)

Clinical Study Protocol EP-002 Final version v3.0 12NOV2020

- 7. Visit 5: steady-state sample pre-dose.
- 8. To be filled in by the patient during, before or after the visits, and at the end of week 2, week 4, and week 8 to follow GI symptoms during the run-in phase.
- 9. To be filled in by the patient before breakfast (at the clinic), then once every hour until lunch (at home).
- 10. To be filled in by the patient at any hour on the day of Visit 2, and at Visit 5 at approximately the same hour (± 1h) as was done at Visit 2.
- 11. IMP administration at the clinic as follows:
 - Visit 2: Placebo capsule during breakfast at the clinic, first randomised IMP dose during lunch at home.
 - Visit 3 and Visit 4: IMP dose during breakfast at the clinic.
 - Visit 5: Last IMP dose during breakfast at the clinic.
- 12. Breakfast at the clinic after weight-related assessments and blood sampling. IMP taken during breakfast.
- 13. Visit 7 applicable for patients giving their separate consent to participate in the follow-up visit.
- 14. New Informed consent required before 6 months follow-up visit. Consent may be collected at any time point prior to any study assessments at Visit 7.
- 15. Visit 7: HbA1c only
- 16. Visit 7: blood pressure only

CONFIDENTIAL 40 (92)

Clinical Study Protocol EP-002 Final version v3.0 12NOV2020

Table 8.1-4 Detailed schedule of events for Visit 2 to 5

Category	Visit	Refer to									Visit 3	3 to 5			
		CSP Section	A	t the clini	ic		At home		At	At the clinic			At home		
	Assessment		Before breakfast	00:00	01.00	02:00	03:00	04:00	Before breakfast	00:00	01.00	02:00	03:00	04:00	
Screening and	Incl./excl. criteria	11.3.2	X												
demographics assessments	Brief physical examination	11.6.2.2	X						X						
	Alcohol breath test	11.3.7	X						X						
	Pregnancy test ¹	11.3.8	X						X						
Weight-related	Weight	11.4.1	X						X						

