9.8.2 Liver chemistry withdrawal criteria

Liver chemistry threshold stopping criteria have been designed to assure patient safety and to evaluate liver event aetiology. Study treatment will be stopped for the individual patient if any

CONFIDENTIAL 51 (92)

of the following liver chemistry stopping criteria, defined in the U.S. Food and Drug Administration (FDA) Guidance on Drug-Induced Liver Injury [34] is met:

• ALT 3 x Upper Limit of Normal (ULN) and total bilirubin $\ge 2x$ ULN (>35% direct bilirubin); **or** ALT 3xULN and INR > 1.5)

NOTE: plasma bilirubin fractionation will be performed.

- ALT 5xULN.
- ALT 3xULN if associated with symptoms (new or worsening) believed to be related to hepatitis (such as fatigue, nausea, vomiting, right upper quadrant pain or tenderness or jaundice) or believed to be related to hypersensitivity (such as fever, rash or eosinophilia).
- Patients with ALT 3xULN and < 5xULN and bilirubin < 2xULN, who do not exhibit hepatitis symptoms or rash, will be allowed to continue study treatment as long as their liver status is monitored weekly for 4 weeks.

If ALT is still $\geq 3xULN$ after 4 weeks of continued treatment, the treatment will be stopped. Approximately 4 weeks after stop of treatment, subjects will be scheduled for an safety follow-up visit (corresponding to Visit 6) for follow-up safety assessments including safety laboratory sampling.

In case the liver enzyme parameters have not returned to baseline levels at the safety follow-up visit (2 weeks after end of treatment), subjects will be referred to their general practitioner for continued follow-up by standard medical/clinical care.

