10.3 Conditions for storage

Both EMP16-02 60/20 and EMP16-02 90/30 capsules should be stored in the fridge (2°C to 8°C) to prolong stability to up to 12 months. Single capsules can be stored at room temperature for a maximum of 12 h.

At temperatures above 40°C, the G3 fraction containing or listat can melt, which may affect the granulation of the fraction and as such the release of or listat and the efficacy of the IMP. This may result in gastrointestinal symptoms. No toxic degradation products have been observed in stability tests.

10.4 **Preparation and accountability**

Each site and the Investigator will maintain a Storage and Accountability Log as well as a Drug Dispensing Log detailing the dates and quantities of study medication received and used by each patient, and study medication destroyed at the safety follow-up visit (Visit 6). Any discrepancies between prepared and returned IMP must be explained and documented. Products deliberately and/or accidentally destroyed by the site or the patient must be accounted for.

CONFIDENTIAL 54 (92)

10.5 **Treatment administration**

The patients will be treated with IMP for a period of 26 weeks.

At the clinic, the IMP will be dispensed by site staff, *e.g.*, a study nurse, directly from the individually packed boxes. At home, the patients will self-administer the IMP. The IMP should be taken halfway into a meal, with approximately 100-200 mL water or other drink. The patient should be instructed to not take more than 200 mL water or other drink during the meal, as this can affect the efficacy of the IMP.

The IMP should preferably be taken halfway through each of the three main meals during the day, but can be taken up to 1 hour after the meal. If a dose of EMP16-02 is missed more than 1 hour from the start of the meal, the dose should not be taken. The IMP should not be taken on an empty stomach. If the patient is not eating three main meals on a day, the IMP can be taken with a lighter snack as well. The patients will be recommended to leave 3-4 h between each meal/IMP dose.

The first IMP dose will be taken at home in association with lunch (or other main meal following breakfast) on Day 1 (after Visit 2). One placebo capsule will be given to all patients in association with breakfast at the clinic on Day 1 (Visit 2).

The last dose will be taken at the clinic in association with breakfast on Day 179±3 days (Visit 5, week 26; in total one dose on Day 179).

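### The 26-week safety endpoint for ECG and most safety laboratory parameters has no scheduled on-treatment measurement: the only post-baseline values come two weeks after the last dose

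*Protocol*

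**What the plan says.** The synopsis and Table 7.4-1 of the protocol give the endpoint as "Clinically significant relative (%) and absolute changes from baseline in safety laboratory parameters and electrocardiogram (ECG) after 26 weeks of treatment". The same sentence continues with vital signs after 7, 14 and 26 weeks. The parent objective in Section 7.2 concerns safety and tolerability during the 26-week treatment period.

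In Table 8.1-3, the rows for the full safety laboratory profile and the 12-lead ECG are marked under Visit 1 and Visit 6 only. Footnote 5 fits this: "Fasting is not required prior to Visit 1 and Visit 6". Table 8.1-4, the detailed plan for Visits 2 to 5, has no row for either, although Section 11.6.4 refers to it for ECG timing.

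Section 10.5 fixes the end of dosing at Visit 5: "The last dose will be taken at the clinic in association with breakfast on Day 179±3 days". Visit 6 is at Week 28, Day 193 ± 3 days.

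The liver panel at Visits 2 to 5 is given in footnote 6 to Table 8.1-3, and again in Table 11.6-2: "Liver enzymes: ALT, AST, ALP, GGT". Section 9.8.2 uses more than these enzymes. One stopping criterion pairs ALT with total bilirubin, another is "ALT 3xULN and INR > 1.5", and the provision for continuing treatment also refers to bilirubin.

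**The concern.** The endpoint asks about the state of patients after 26 weeks on drug. For ECG, haematology, coagulation, renal function, electrolytes, bilirubin and urinalysis, the only scheduled post-baseline value in a completer is taken after about two weeks off drug. Reported under the endpoint's present label, those values would be read as week-26 on-treatment safety. A change that was present on treatment and had reversed by Visit 6 would not appear in the scheduled data, and nothing in the table would tell the reader so. A statistical analysis plan cannot repair this, because it cannot analyse measurements that were never scheduled.

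A second, smaller mismatch concerns Section 9.8.2. It relies on total bilirubin and INR during treatment, but neither is in the schedule for Visits 2 to 5.

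**Working it through.** **1. Time from last dose to the only post-baseline ECG and full profile**

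Inputs: last dose on Day 179 ± 3 (Section 10.5, Table 8.1-3); Visit 6 on Day 193 ± 3 (Table 8.1-3).

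- Nominal: 193 − 179 = 14 days. This reproduces the two weeks stated in Section 8.1.
- Shortest, windows independent: (193 − 3) − (179 + 3) = 190 − 182 = 8 days.
- Longest, windows independent: (193 + 3) − (179 − 3) = 196 − 176 = 20 days.
- If Visit 6 is instead counted from each patient's actual last dose: 14 ± 3 = 11 to 17 days.

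On every reading the value is off drug.

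**2. Which parameters have a scheduled on-treatment value**

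The on-treatment visits are Visits 3, 4 and 5. Visit 2 is the baseline visit: its blood sampling precedes breakfast and the first randomised dose is taken later that day, so it does not count.

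Table 11.6-1 lists 14 chemistry, 5 haematology and 2 coagulation analytes. Total and conjugated bilirubin count as one, as do the white cell count and its differential; FSH and the pregnancy test are left out. 14 + 5 + 2 = 21.

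| Scheduled at Visits 3 to 5 | Not scheduled at Visits 3 to 5 |
|---|---|
| ALT, AST, ALP, GGT (liver panel) | bilirubin, calcium, creatinine, phosphate, potassium, sodium, urea |
| albumin, glucose, HbA1c (efficacy marker panel) | haematocrit, haemoglobin, platelets, red cells, white cells |
| | APTT, INR |
| 7 analytes | 7 + 5 + 2 = 14 analytes |

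7 + 14 = 21, so two thirds of the blood analytes have no scheduled on-treatment sample. The 12-lead ECG and the urine dipstick have none either: 0 of 3 on-treatment visits.

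**3. What the endpoint sentence means by weeks of treatment**

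The sentence gives Weeks 7, 14 and 26 for vital signs. Table 8.1-3 takes vital signs at Visit 3 (Week 7), Visit 4 (Week 14) and Visit 5 (Week 26), all on treatment. In that sentence, then, 26 weeks means Visit 5. Visit 6 is labelled Week 28.

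**4. Planned reporting**

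Section 17.7.5 promises change from baseline at each visit for safety laboratory data. For the 14 analytes there is one scheduled pre-dose value (screening, which is baseline under the definition in Section 17.1) and one scheduled post-baseline value (Visit 6). The summary for these parameters is therefore a single screening-to-follow-up comparison.

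**5. Section 9.8.2 against the schedule**

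- ALT is scheduled at Visits 3 to 5, so the trigger of each criterion is measured.
- Total bilirubin and INR are in Table 11.6-1 (Visits 1 and 6) but not in Table 11.6-2 (Visits 2 to 5).
- A note in Section 9.8.2 says that bilirubin fractionation will be done, and the section provides weekly monitoring of liver status in some patients. It gives no timing for the bilirubin sample relative to the ALT result, and no procedure or timing for INR.

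**The case against.** The strongest defence is that the schedule was chosen by risk. Section 6.3 argues that plasma exposure to both components is low and systemic effects very unlikely. It gives rare liver effects of acarbose as the reason for measuring liver function at every visit. Seven safety analytes and the vital signs are followed on treatment, ECG and laboratory reporting is descriptive (Sections 17.7.4 and 17.7.5), and this is one secondary endpoint of an exploratory Phase IIa trial. All of that stands, and it bears on how much the gap matters. It does not make a Week 28 measurement a Week 26 one. The phrase could be stretched to mean after treatment has been completed, but that fits poorly with the Weeks 7, 14 and 26 in the same sentence.

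Three stronger readings are tempting and are not supported:

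- **That there are no on-treatment safety laboratory data.** Seven of the 21 analytes are sampled at Visits 3 to 5, including Week 26.
- **That the liver stopping rule cannot be applied.** The bilirubin and INR criteria both start from ALT, which is scheduled. Section 9.8.2 foresees event-driven testing, and two of its stopping criteria (ALT at 5 times ULN, and ALT at 3 times ULN with symptoms) need neither bilirubin nor INR. What is missing is a statement of where and when those two values are obtained.
- **That the protocol itself says laboratory or ECG effects would have gone by Visit 6.** Section 6.3 does say that "these side-effects are transient and will quickly resolve if patients stop taking the drugs", but this follows a list of mainly gastrointestinal symptoms, with headache, nausea and upper respiratory infections. It is no evidence on how fast laboratory or ECG changes reverse.

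**Conclusion.** The endpoint wording and the schedule disagree. For ECG, urinalysis and 14 of 21 blood analytes, the endpoint promises change after 26 weeks of treatment while the scheduled data show change from screening to about two weeks off drug (nominally 14 days; 8 to 20 with independent windows). For ALT, AST, ALP, GGT, albumin, glucose, HbA1c and vital signs, on-treatment values are scheduled and the endpoint can be met.

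The count rests on the visit marks in Table 8.1-3 as read from the document; footnote 5 and the absence of these rows from Table 8.1-4 agree with them. It concerns scheduled assessments only: unscheduled tests during treatment are possible, and patients who withdraw early have the Visit 6 procedures at another time. Whether any reversible effect would in fact be missed is not known from the protocol.

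The consequence is limited to what the trial can claim about on-treatment safety. The primary endpoint, the sample size and the error rates do not change. The Section 9.8.2 mismatch is a point to reconcile, not a rule shown to be unworkable.

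**What to change.** - **At minimum, re-label.** In the synopsis and Table 7.4-1, split the endpoint. For ECG, urinalysis and the parameters not sampled at Visits 3 to 5, state the time point as two weeks after end of treatment, and label the corresponding tables in the same way. Adjust Section 17.7.5 so that the reference to each visit matches the visits at which each parameter is taken, and correct the pointer to Table 8.1-4 in Section 11.6.4. This changes text only.
- **If the 26-week wording is to stay, add.** Schedule the ECG and the routine panel at Visit 5, where patients already attend fasting and give blood, and keep both at Visit 6. The cost is one ECG and one routine panel per patient, plus a schedule amendment. Patients who have already passed Visit 5 would not be covered, so the re-labelling would still apply to them. Moving the tests instead of adding them would not be free: the Visit 6 procedures also serve patients who withdraw early (footnote 2 to Table 8.1-3, Section 9.8.3) and follow-up after a liver-related stop (Section 9.8.2).
- **Separately, reconcile Section 9.8.2 with Tables 8.1-3 and 11.6-2.** State where and when total bilirubin and INR are obtained during treatment. No clinical rule is proposed here; the passages need to agree.

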8 STUDY DESIGN

8.1 Overall study design and schedule of events

This is an exploratory, randomised, double-blind, placebo-controlled study to evaluate the effect of two different doses of EMP16-02 on body weight loss in overweight and obese patients. EMP16-02 will be taken orally three times daily (TID) together with three daily meals for a period of 26 weeks. For detailed information about treatment administration, see Section 10.5.

An overview of the study design is shown in Figure 8.1-1.

Figure 8.1-1 Overview of the study design

The study will be conducted at two study centres in Sweden. A total of 156 randomised patients are expected to participate in the main part of the study for approximately 32 weeks, including a screening period of up to 4 weeks, a 26-weeks treatment period and a safety follow-up visit 2 weeks after the last dose. Patients giving their consent to participate in a 6 month follow-up evaluation will participate in the study for 58 weeks including a screening period of up to 4 weeks, 26 weeks of treatment, a safety follow-up visit 2 weeks after the last treatment and a follow-up visit 26 weeks after the last treatment.

EMP16-02 will be given to obese patients with an initial BMI \geq 30 kg/m² or \geq 28 kg/m² in the presence of other risk factors (e.g., hypertension, glucose dysregulation such as impaired glucose tolerance and T2DM, and/or dyslipidaemia). Prior to any study assessments, patients will be asked to provide signed informed consent to participate in the study. The main part of the study consists of 6 visits to the research clinic, including screening and a safety follow-up visit. Visit 7 will be a long-term follow-up visit scheduled 6 months after completion of the 26-weeks treatment. All patients completing the treatment period will be asked to participate in the long-term follow-up and a separate consent will be collected. There will be no overnight stays at the clinic. Screening (Visit 1) will take place from Day -28 to Day -1. An electronic diary will be used to provide the patients with questionnaires to be filled in during or shortly before/after the visits. At two extra occasions between Visit 4 and 5, the electronic diary will be used for collecting information on IMP compliance, AEs and use of concomitant medication

CONFIDENTIAL 33 (92)

Clinical Study Protocol EP-002 Final version v3.0 12NOV2020

Eligible and consenting patients will arrive at the research clinic in the morning of the first dosing day (Day 1, Visit 2) after at least 8 hours overnight fasting. A re-check of eligibility including a brief physical examination, vital signs and assessment of body weight will be conducted.

The patients will be randomised to either of two doses of EMP16-02 or placebo:

- 1. EMP16-02 120 mg O/40 mg A
- 2. EMP16-02 150 mg O/50 mg A
- 3. Placebo (identical capsules)

Blood sampling (fasting), and anthropometric measurements will be performed. Patients will receive electronic diary instructions and will be asked to fill in a satiety and craving questionnaire before breakfast (at the clinic), and then once every hour for 4 hours until before lunch (at home). A standardised breakfast will be served at the clinic. Halfway through breakfast at Visit 2, all patients will receive a placebo capsule independent of the treatment arm to which the patients have been randomised, to provide the patients with the opportunity to train on self-administering the IMP under supervision of clinic staff. The patients will also receive instructions for filling in more questionnaires regarding health and quality of life, meal pattern, activity and sleep, and gastrointestinal symptoms (gastrointestinal rating scale [GSRS], as outlined in Section 11.5.4.

The patients will be instructed to take EMP16-02 or placebo halfway through each meal, together with approximately 100-200 mL water (or other drink) on all subsequent treatment days. Once IMP has been handed out, the patients are free to leave the clinic. The first randomised IMP dose will be taken during lunch (or the next meal) at home. See Table 8.1-4 for a detailed schedule of events for Visit 2.

Patients randomised to EMP16-02 will start with a run-in period of 6 weeks during which the dose is sequentially increased. From week 7, all patients will have reached their final intended dose and a 20-week treatment and observation period will start. The run-in phase will start at a dose of 60 mg O and 20 mg A TID, which will sequentially be increased with 30 mg O/10 mg A every two weeks until the target doses of 120 mg O/40 mg A TID (for the lower dose group) and 150 mg O/50 mg A TID (for the higher dose group) are reached. The dosing regimen is summarised in Table 8.1-1.

Table 8.1-1 Increasing dosing regimen

Target dose	Week 1 and 2	Week 3 and 4	Week 5 and 6	Week 7 to 26
EMP16-02 120 mg O/40 mg A	60 mg O/20 mg A	90 mg O/30 mg A	120 mg O/40 mg A	120 mg O/40 mg A
EMP16-02 150 mg O/50 mg A	60 mg O/20 mg A	90 mg O/30 mg A	120 mg O/40 mg A	150 mg O/50 mg A

CONFIDENTIAL 34 (92)

EMP16-02 is formulated in capsules available in two strengths:

- EMP16-02-90/30, containing 90 mg O/30 mg A
- EMP16-02-60/20, containing 60 mg O/20 mg A

Placebo treatment consists of matching, oral capsules. Placebo and EMP16-02 capsules need to be taken TID together with the three main daily meals according to the schedule displayed in Table 8.1-2.

Target dose	Week 1 and 2	Week 3 and 4	Week 5 and 6	Week 7 to 26
EMP16-02 120 mg O/40 mg A	1x EMP16-02- 60/20	1x EMP16-02- 90/30	2x EMP16-02- 60/20	2x EMP16-02- 60/20
EMP16-02 150 mg O/50 mg A	1x EMP16-02- 60/20	1x EMP16-02- 90/30	2x EMP16-02- 60/20	1x EMP16-02- 60/20 1x EMP16-02- 90/30
Placebo	1x placebo capsule	1x placebo capsule	2x placebo capsule	2x placebo capsule

Table 8.1-2 Number and type of capsules to be taken

During the run-in phase, after 2, 4, (6) and 8 weeks, patients will fill in the GSRS questionnaire using the electronic diary.

Patients will come to the clinic at Visit 3 (week 7), Visit 4 (week 14) and Visit 5 (week 26) for safety assessments and assessments of weight and anthropometric measurements, as outlined in Table 8.1-3 and detailed in Table 8.1-4. Patients will arrive in the morning after at least 8 hours overnight fasting. All visits will start with a brief physical examination followed by blood sampling (fasting) and assessment of body weight and body composition. A standardised breakfast will be served during which the patient will take the IMP. All or a selection of the questionnaires, including the satiety and craving questionnaire, will be filled in in a similar way as during Visit 2, see Table 11.5-2 scheduling of the questionnaires.

After 18 and 22 weeks of treatment (Day 123 ± 3 days and Day 151 ± 3 days respectively), patients will be asked to answer questions about IMP compliance, occurrence of AEs and use of concomitant medication using an electronic diary.

New IMP will be handed out to the patients at Visit 2, 3 and 4.

At Visit 5 (week 26), the patients will take the last dose during breakfast. Visit 6 is a safety follow-up visit. Visit 7 is a 6 month follow-up visit for consenting patients who has completed the 26-week treatment period with active EMP16-02 treatment (120 mg O/ 40 mg A and 150 mg O/50 mg A) or placebo.

Efficacy assessments include:

- Weight (Section 11.4.1)
- Other anthropometric measurements: BMI, waist circumference, sagittal diameter, bio-impedance (Section 11.5.1)
- Blood sampling for fasting lipid metabolism, glucose metabolism and inflammation markers (Section 11.5.2)

CONFIDENTIAL 35 (92)

Clinical Study Protocol EP-002 Final version v3.0 12NOV2020

- Blood pressure (Section 11.5.3)
- Questionnaires (Section 11.5.4): meal pattern (Section 11.5.4.1), GSRS (Section 11.5.4.2), satiety and craving (Section 11.5.4.3), activity and sleep (Section 11.5.4.4) and health and quality of life (RAND-36, Section 11.5.4.5)
- Drop-out rate (Section11.5.5, assessed both in terms of safety and efficacy)

Safety assessments include:

- AE recording (Section 11.6.1)
- Vital signs (Section11.6.3, blood pressure assessed both in terms of safety and efficacy)
- ECG (Section 11.6.4)
- Fasting safety laboratory blood sampling (Section 11.6.5)
- Physical examination (Section 11.6.2)
- GSRS (Section 11.5.4.2, assessed both in terms of safety and efficacy)

Exploratory assessments include:

- Fasting blood sampling for ApoA1 and ApoB (Section 11.7.1)
- Pre-dose blood sampling for orlistat and acarbose plasma concentrations at steady state (Section 11.7.2)
- Weight 6 months after end of treatment (Section 11.4.1)
- HbA1c 6 months after end of treatment (Section 11.5.2)
- Blood pressure 6 months after end of treatment (Section 11.6.3)

For timing of assessments, refer to the schedule of events in Table 8.1-3. Details for Visit 2 to Visit 5 are provided in Table 8.1-4.

CONFIDENTIAL 36 (92)

Clinical Study Protocol EP-002 Final version v3.0 12NOV2020

Table 8.1-3 Schedule of events

Category	Visit	Refer to CSP		Main part							
		Section	Screening		Safety follow-up	part 6 month follow-up					
			Visit 1	Visit 2 ¹	Visit 3 ¹	Visit 4 ¹	Visit 5 ¹	Visit 6	Visit 7 ¹³		
			Morning visit	Morning visit	Morning visit	Morning visit	Morning visit	Morning visit	Morning visit		
	Assessment		Day -28 to Day -1	Week 1	Week 7	Week 14	Week 26	Week 28 ²	Week 52 (±2 weeks)		
				Day 1 Baseline	Day 46 (±3 days)	Day 95 (±3 days)	Day 179 (±3 days)	Day 193 (±3 days)			
Screening and	Informed consent	11.3.1	X						X^{14}		
demographics	Inclusion/exclusion criteria	11.3.2	X	X							
assessments	Demographics	11.3.3	X								
	Medical/obesity history	11.3.4	X								
	Full physical examination	11.6.2.1	X								
	Brief physical examination	11.6.2.2		X	X	X	X	X			
	HIV, hepatitis B and C	11.3.6	X								
	Alcohol breath test	11.3.7	X	X	X	X	X	X			
	Pregnancy test ³	11.3.8	X	X	X	X	X	X			
	Urine drug screen ⁴	11.3.9	X					X			
Weight-related	Weight	11.4.1	X	X	X	X	X		X		
assessments	Height	11.5.1.1	X								
	BMI	11.5.1.1	X	X		X	X		X		
	Waist circumference	11.5.1.2	X	X	X	X	X				
	Sagittal diameter	11.5.1.3	X	X	X	X	X				
	Bio-impedance	11.5.1.4		X	X	X	X				

CONFIDENTIAL 37 (92)

Clinical Study Protocol EP-002 Final version v3.0 12NOV2020

Category Visit		Refer to CSP		Follow-up part					
		Section	Screening		Safety follow-up	6 month follow-up			
			Visit 1	Visit 2 ¹	Visit 3 ¹	Visit 4 ¹	Visit 5 ¹	Visit 6	Visit 7 ¹³
			Morning visit	Morning visit	Morning visit	Morning visit	Morning visit	Morning visit	Morning visit
	Assessment		Day -28 to Day -1	Week 1	Week 7	Week 14	Week 26	Week 28 ²	Week 52 (±2 weeks)
				Day 1 Baseline	Day 46 (±3 days)	Day 95 (±3 days)	Day 179 (±3 days)	Day 193 (±3 days)	
Blood and urine sampling	Full safety laboratory profile ⁵	11.6.5	X					X	
(fasting)	Liver function ⁶	11.6.5		X	X	X	X		
	HbA1c, glucose, insulin, triglycerides, total cholesterol, LDL, HDL, Hs-CRP, albumin	11.5.2		X	X	X	X		X ¹⁵
	Exploratory: ApoA1, ApoB	11.7.1		X	X	X	X		
	Exploratory: Blood sampling for orlistat and acarbose plasma levels ⁷	11.7.2					X		
Vital signs and	Vital Signs	11.6.3	X	X	X	X	X	X	X ¹⁶
ECG	12-lead ECG	11.6.4	X					X	
Questionnaires	Meal pattern	11.5.4.1		X	X	X	X		
	GI tolerability (GSRS) ⁸	11.5.4.2		X	X	X	X		
	Satiety and craving ⁹	11.5.4.3		X	X	X	X		
	Activity and sleep	11.5.4.4		X	X	X	X		
	Health and quality of life RAND-36 ¹⁰	11.5.4.5		X			X		

CONFIDENTIAL 38 (92)

Clinical Study Protocol EP-002 Final version v3.0 12NOV2020

Category Visit		Refer to CSP			Main	part			Follow-up part
		Section	Screening			Safety follow-up	6 month follow-up		
			Visit 1	Visit 2 ¹	Visit 3 ¹	Visit 4 ¹	Visit 5 ¹	Visit 6	Visit 7 ¹³
			Morning visit	Morning visit	Morning visit	Morning visit	Morning visit	Morning visit	Morning visit
Assessment	Assessment		Day -28 to Day -1	Week 1	Week 7 Day 46 (±3 days)	Week 14 Day 95 (±3 days)	Week 26 Day 179 (±3 days)	Week 28 ² Day 193 (±3 days)	Week 52 (±2 weeks)
				Day 1 Baseline					
IMP	Randomisation	9.9		X					
	Dispense IMP			X	X	X			
	IMP administration at clinic ¹¹	10.5		X	X	X	X		
	IMP compliance	10.7			X	X	X		
Food	Standardised breakfast ¹²			X	X	X	X		
Patient	Diary instruction	11.2		X					
instructions	Diet recommendations	9.6.1.2		X					
AEs and	Baseline symptoms	11.3.10	X	X					
medication	AEs	11.6.1				X			
	Prior and concomitant med.	11.3.5				X			

CSP=Clinical study protocol, HIV=Human immunodeficiency virus.

- 1. For detailed schedule of events, see Table 8.1-4.
- 2. At Visit 6 or after early withdrawal.
- 3. Women of child-bearing potential (WOCBP) only, urine test.
- 4. Drug tests may also be performed at additional random occasions during the study.
- 5. Full safety laboratory profile: Clinical chemistry, haematology, coagulation, urinalysis (dip stick). Fasting is not required prior to Visit 1 and Visit 6.

6. Liver enzymes: ALT, AST, ALP, GGT.

CONFIDENTIAL 39 (92)

Clinical Study Protocol EP-002 Final version v3.0 12NOV2020

- 7. Visit 5: steady-state sample pre-dose.
- 8. To be filled in by the patient during, before or after the visits, and at the end of week 2, week 4, and week 8 to follow GI symptoms during the run-in phase.
- 9. To be filled in by the patient before breakfast (at the clinic), then once every hour until lunch (at home).
- 10. To be filled in by the patient at any hour on the day of Visit 2, and at Visit 5 at approximately the same hour (± 1h) as was done at Visit 2.
- 11. IMP administration at the clinic as follows:
 - Visit 2: Placebo capsule during breakfast at the clinic, first randomised IMP dose during lunch at home.
 - Visit 3 and Visit 4: IMP dose during breakfast at the clinic.
 - Visit 5: Last IMP dose during breakfast at the clinic.
- 12. Breakfast at the clinic after weight-related assessments and blood sampling. IMP taken during breakfast.
- 13. Visit 7 applicable for patients giving their separate consent to participate in the follow-up visit.
- 14. New Informed consent required before 6 months follow-up visit. Consent may be collected at any time point prior to any study assessments at Visit 7.
- 15. Visit 7: HbA1c only
- 16. Visit 7: blood pressure only

CONFIDENTIAL 40 (92)

Clinical Study Protocol EP-002 Final version v3.0 12NOV2020

Table 8.1-4 Detailed schedule of events for Visit 2 to 5

Category	Visit	Refer to									Visit 3	3 to 5			
		CSP Section	A	t the clini	ic		At home		At	At the clinic			At home		
	Assessment		Before breakfast	00:00	01.00	02:00	03:00	04:00	Before breakfast	00:00	01.00	02:00	03:00	04:00	
Screening and	Incl./excl. criteria	11.3.2	X												
demographics assessments	Brief physical examination	11.6.2.2	X						X						
	Alcohol breath test	11.3.7	X						X						
	Pregnancy test ¹	11.3.8	X						X						
Weight-related	Weight	11.4.1	X						X						
